**Trial centres should notify SCTRUM one week in advance of any planned surgery.**

### **3.3. Paraffin Embedded Tissue Sections**

Paraffin embedded core biopsies that are no longer needed by the local pathologist for diagnostic purposes may be requested for use in translational work, following discussion with the local site consultant pathologist.

### **3.4. Blood and Urine Processing**

Patients should be fasted for 6 hours prior to urine sampling. Therefore, it is suggested that blood and urine sampling is performed as early in the morning as clinically feasible, and the times of the patient's last meal and last axitinib should be recorded.

#### **3.4.1. Blood Samples**

Blood - Venous blood for biomarker analysis will be collected in ethylenediaminetetraacetic acid (EDTA) tubes. **Two** 10ml tubes will be collected on day 1 week 1 prior to starting axitinib treatment, **two** tubes at the week 3 clinic visit, **two** tubes at the week 5 clinic visit, **two** tubes at the week 7 clinic visit, **two** at time of nephrectomy and **two** tubes at 12 weeks post surgery follow up. All blood samples must be processed locally. Blood samples must be centrifuged and processed for whole blood and plasma within 1 hour of blood sampling, and within 4 hours of blood sampling for collection of buffy coat and peripheral blood mononuclear cells (PBMCs) from the remaining blood. Detailed instructions for blood processing are contained in the NAXIVA laboratory manual. From these two EDTA tubes the following samples must be collected:

**Whole blood (WB) – all centres:** Immediately after blood sampling gently invert the tubes 8-10 times to mix and leave tubes upright prior to further processing. From one of EDTA tubes, remove 1ml whole blood and place into a screw cap cryovial (labelled with 'WB, patient's trial number and the date). Snap freeze the tube in liquid nitrogen and store at -80°C at the trial centre until transfer to University of Cambridge on dry ice.

**Plasma (P) – all centres:** This step **must be completed within 1 hour** of blood sampling. Following transfer of whole blood from one vacutainer, spin both vacutainer tubes at 1600g for 10 min at room temperature using a "swing-out" rotor. Transfer 1ml aliquots of plasma to sterile 2ml micro-tubes (non-screw capped RNase-free tubes can be used at this stage). Take care to avoid any buffy coat layer in this step. Centrifuge the plasma aliquots in a bench top centrifuge at 14,000rpm for 10 minutes at 4°C to pellet any remaining cellular debris. Carefully transfer 1ml aliquots of supernatant to labelled (P/patient's trial number/date) sterile 1.8ml screw-capped cryovials, and discard the pellet. Store the original vacutainers with remaining blood at 4°C for collection of buffy coat or Peripheral Blood Mononuclear Cells (PBMCs). Aim to collect 4 cryovials with roughly even amounts of plasma in each. Store at -80°C at the trial centre until transfer to University of Cambridge on dry ice. **All plasma samples MUST be double-spun using the NAXIVA protocol above to allow down-stream translational assays to be performed.**

**Buffy coat (BC)**

**For collection ONLY by sites NOT processing samples for PBMCs (as this step removes the PBMCs):** Following removal of whole blood and plasma from the vacutainers, remove the buffy coat with about 100ul of plasma taking care not to lift the red cells. Optional: If it is difficult to cleanly separate the buffy coat layer, combine the buffy coats from both vacutainers in a small Eppendorf tube/micro centrifuge tube and centrifuge at 10,600g for 2 minutes. Then aliquot into 1 x labelled cryovial (BC/patient's trial number/date). Store at -80°C at the trial centre until transfer to University of Cambridge on dry ice.

**Peripheral blood mononuclear cells (PBMCs)**

**Do NOT collect buffy coat if processing blood for PBMCs as buffy coat contains PBMCs resulting in very low yield using this protocol.**

This method requires the use of SepMate tubes, ficoll, and 'freezing mix' which will be provided to selected sites by the SCTRUS as part of the sample collection kits. All processing steps (including removal of plasma from vacutainers) MUST be carried out under sterile conditions eg. HEPA filtered CL2-certified tissue culture facilities, if blood samples are being used to isolate PBMCs.

1. Ideally this step must be completed within 4 hours of blood sampling, but certainly completed same day. If unable to process samples immediately after plasma extraction, store samples at 4°C.
2. After removing plasma dilute the remaining blood in the tube 1:1 with pre-warmed (room temperature) sterile phosphate buffered saline (PBS) (if a full 10ml EDTA tube was taken from the patient the volume of PBS to add will be approximately 4ml).
3. Mix tube well by inverting 3 times.
4. Keeping the SepMate tube upright, pipette 15ml Ficoll through the central hole of the insert in the SepMate tube. The top of the Ficoll will come to ABOVE the level of the insert. Air bubbles may be seen under the insert and are reduced by pipetting the Ficoll more slowly through the insert, but don't affect the cell separation.
5. Quickly pipette the blood/PBS mix down the side of the SepMate tube.
6. Centrifuge tubes at 1200g (2800 rpm) for 10 minutes at room temperature (using normal brake settings ie brake on).
7. Remove tubes from centrifuge and collect the mononuclear cells by inverting the SepMate tube into a 50ml Falcon tube in one smooth movement. Do not hold the SepMate tube inverted for >2 seconds or the red cells (which may be seen on the surface of the SepMate insert before inversion in addition to the bottom of the tube) start to dribble through the insert and will contaminate the mononuclear cells.
8. Dilute mononuclear cells to 45ml with pre-warmed PBS.
9. Centrifuge tubes at 1200g (2800 rpm) for 10 minutes at room temperature (normal brake settings) to wash the cells.
10. Discard supernatant (carefully as cell pellet may be slimy).
11. Resuspend cell pellet in 2ml 10% dimethylsulfoxide in fetal calf serum ('freezing mix') and freeze 4 labelled (PBMC/patient's trial number/date) cryovials of PBMCs (aliquot equal volumes into each cryovial and record volumes).
12. Immediately place at -80°C (in a pre-cooled (4°C) [name]/ similar container). NB check isopropanol level beforehand. Store at -80°C for up to a week, and then transfer to liquid nitrogen until transfer on dry ice to University of Cambridge.

**3.4.2. Urine Samples- all centres**

Urine samples will be collected on day 1 week 1, week 3, week 5, week 7 at nephrectomy and 12 week post surgery follow-up.

15ml of urine (ideally after patient fasted for 6 hours, fasting time to be noted) should immediately be stored at -80°C at trial centres until transfer to University of Cambridge on dry ice.

In addition, 30ml urine in a falcon tube should have EDTA added immediately to prevent nuclease degradation (for cfDNA analysis). Add 600ul of 0.5M EDTA and gently invert 8-10 times. Centrifuge at 3000g for 10 minutes within 1 hour of collection to remove cellular debris. Transfer 3.6ml aliquots of supernatant to fresh sterile 4ml cryotubes. Retain cell pellet, suspended in 1ml urine.

Each specimen container should be labelled as specified in the NAXIVA laboratory manual. Labels will be supplied by the SCTRUs as part of the sample collection kits.

#### 4. Storage and Collection of Samples

Blood, urine and tissue samples should be stored at local trial centres in a -80°C freezer and transferred in batches as detailed in the NAXIVA laboratory manual to the University of Cambridge on dry ice unless part of the fresh tissue for immunophenotyping/ cell culture study. Samples which are part of the fresh tissue for immunophenotyping/ cell culture study MUST be stored at 4°C and couriered to University of Cambridge in insulated polystyrene containers with ice packs in situ as soon as possible after collection (certainly within 24 hours of collection but ideally same day). Further details for transfer of these samples can be found in the NAXIVA laboratory manual.

##### 4.1. Translational sample Schedule

Visit/Assessment	Within 28 days prior to registration	Week 1	Week 3	Week 5	Week 7	Nephrectomy	12 weeks post surgery follow up
Percutaneous image guided biopsy of non-necrotic region of primary renal tumour (5 cores, 2 to be sent to pathology for formalin-fixation and paraffin embedding of which 1 to be transferred to University Cambridge; 1 core to be snap frozen in liquid nitrogen and stored at -80°C; 2 to be placed in tubes containing media and couriered within 24 hours to University of Cambridge)	X						
Nephrectomy tissue						X	
2 EDTA tube blood samples for whole blood, double-spun to obtain plasma, buffy coat and PBMCs at selected sites (samples to be stored at -80°C)		X	X	X	X	X	X
Urine sample (1 container to be stored at -80°C, 1 sample EDTA treated and spun sample at -80°C)		X	X	X	X	X	X

## 4.2. Sample Tracking

Sites will be required to record the collection of participants' samples by emailing a sample reporting form to the central lab at the University of Cambridge and SCTR. SCTR will provide courier account details for sites to organise transport of the samples.

### 4.2.1. Tracking of baseline samples for ineligible patients

In order to minimise invasive procedures, patients will be consented for the trial prior to obtaining both the standard diagnostic biopsy sample and baseline translational study research biopsies. Patients will be asked to provide consent for the research samples to be sent to the University of Cambridge should histological examination of the diagnostic sample show that the patient is ineligible for NAXIVA. Collection of these samples should be notified to the SCTR by emailing: [[contact]](mailto:[contact])

The following information will be required:

- Centre name
- Confirmation of written informed consent
- Trial ID
- Patient's date of birth

This notification will allow these samples to be tracked by the University of Cambridge and SCTR.

## 4.3 Expedited reporting of fresh tumour collection at biopsy and planned nephrectomy

All participating sites must notify SCTR in advance of the date of planned biopsy or nephrectomy.

Centres should notify SCTR of the biopsy or nephrectomy, by completing the NAXIVA expedited notification of tissue collection form (included within the NAXIVA laboratory manual) and emailing it to: [[contact]](mailto:[contact])

SCTR will then notify University of Cambridge ([name] and [name]) to expect samples.

## 4.4 Tissue Sample processing at the University of Cambridge

All samples will be catalogued in an electronic database at the University of Cambridge. The time from core biopsy collection to snap freezing and from ischaemia to snap freezing for nephrectomy specimens will be recorded on a database. All tissues will be stored in an alarmed and locked -80°C freezer (or liquid nitrogen tank for PBMCs and dissociated tumour samples) which are dedicated to the storage of clinical trial patient samples.

### 4.4.1 Blood Specimens (Whole blood, Plasma, Buffy coat, PBMC)

Analysis of whole blood, plasma, buffy coat, and PBMCs for translational studies will be conducted at the University of Cambridge. Plasma will be analysed for biomarkers (including metabolites, circulating tumour (ct) DNA, and cytokines). DNA will be extracted from whole blood/ or buffy coat and PBMCs for sequencing of host DNA. PBMCs will be immunophenotyped using CyTOF.

### 4.4.2. Urine Specimens

Analysis of urine samples will be conducted at University of Cambridge. Urine will be analysed for biomarkers (including metabolites, circulating tumour (ct) DNA, and cytokines).

### 4.4.3 Core Biopsy and Nephrectomy Specimens

Processing and analysis of core biopsy, nephrectomy and surgical specimens will be conducted at the University of Cambridge. Dissociation of fresh tumour, venous thrombus and normal kidney samples will be performed to separate malignant cells from associated

stromal and immune components, and immunophenotyping will be performed using CyTOF. Cell lines (tumour, stromal, lymphocyte) will be generated if sufficient tissue allows. RNA and DNA from each will be extracted from fresh-frozen samples according to Good Laboratory Practice standards. Immunohistochemistry and immunofluorescence staining will be performed on FFPE samples.

## 5. Analysis of Biosamples

Biosample analysis aims to correlate changes in biomarkers with toxicity and response to axitinib treatment.

The techniques below may be used to explore this endpoint and are based on the current literature. Equivalent novel methods and technologies might be used at the time of analysis.

### 5.1. Metabolomics

It is well established that there is a strong metabolic basis to ccRCC. The presence of the Warburg effect has revealed several novel targets for treatment or tumour surveillance. [name] is an expert in metabolomics, working mainly on inherited forms of kidney cancer. Using LC-MS, metabolites will be assayed in urine, blood and tissue across the various time points of the NAXIVA study to assess the use of these molecules in patients with IVC VTT and with Axitinib therapy. This work will be discovery in nature assessing alterations in metabolic profile within protein from tumour, plasma and urine at sequential time points within the NAXIVA study.

### 5.2. Circulating Tumour DNA

In view of intratumoural heterogeneity, the use of tumour tissue for the development of prognostic and predictive biomarkers in ccRCC is challenging. Circulating tumour DNA (ctDNA) has been established to represent the tumour biology and may be superior to tissue as heterogeneity will be negated. Variant analysis will be undertaken on multi-region sampled issue using exome and shallow whole genome sequencing. A custom capture panel for targeted higher-depth (and higher sensitivity) sequencing of plasma and urine samples will be developed for each patient to assess the feasibility of tracking circulating DNA molecules that harbour somatic mutations. The end-point of this analysis will be to determine the ability to identify variants in both tissue and plasma and the change in ctDNA profiles from baseline to treatment phase to posttreatment phase which may be informative regarding markers of tumour response and minimal residual disease. Further validation studies of any positive findings will be undertaken separately.

### 5.3. Proteomics

Formalin fixed paraffin embedded biopsy and nephrectomy tissue will be utilised in an automated quantified immunohistochemical based analysis of putative markers of response to tyrosine kinase inhibitors. In addition to Ki67 measurement of effect of Axitinib on proliferation, other markers of response to tyrosine kinase inhibitors will be evaluated. In recent work, it has been established that modulation of CA9 protein levels occurs following sunitinib therapy in metastatic clear cell RCC (ccRCC); this effect will be validated using patient samples from NAXIVA. The outcome of this work will be to establish a link between expression of these proteins and reduction in height of the VTT with axitinib. If a correlation is established these proteins will be helpful as surrogate translational endpoints in future ccRCC neoadjuvant studies.

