## 3. TRIAL DESIGN

### 3.1. General Design

NAXIVA is a single arm, single agent, open label, phase II feasibility study of axitinib in patients with both metastatic and non-metastatic renal cell carcinoma of clear cell histology. 20 patients will be recruited from multiple centres within the United Kingdom.

Patients who have signed informed consent and who have met all eligibility criteria will be registered into the trial.

The starting dose of axitinib will be 5mg BID and escalated to 7mg BID and then 10mg BID. A dose modification assessment will take place every 2 weeks in clinic during the 8 week pre-surgical treatment period and will be dependent on tolerability of treatment. Patients will follow an aggressive axitinib dose escalation process within the 8 week period to a maximum of 10mg BID. Patients should stop axitinib a minimum of 36 hours and a maximum of 7 days prior to surgery in week 9.

Blood, urine and tissue samples will be taken prior to and during therapy to evaluate biomarkers of treatment response. Nephrectomy and IVC tumour thrombectomy will be planned for all patients on the trial.

Response to axitinib in VTT, primary tumour and any RECIST measureable lesion will be correlated with changes in molecular markers.

Patients will be followed up in clinic at 6 & 12 weeks post surgery.

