### **Primary Safety Endpoints**

Thirteen patients will be recruited at first; if at least 1 patient has an improvement in the Mayo classification a further 7 patients would be recruited (to the final total of 20 patients who have received study drug), to receive study drug. At least 3 patients showing reductions in Mayo score are required for a positive trial. The early stopping rules are:

- (1) If a single M0 patient progresses to the point where surgery is no longer possible, then recruitment of new patients will be suspended following a review by the data monitoring committee (DMC).
- (2) If a single M0 patient becomes M1 recruitment of new patients will be suspended following a review by the DMC.
- (3) If in 3 patients the VTT extends but patients remain surgically resectable the trial will close. If the VTT has extended the patient will be expedited and operated on as soon as possible.

Where there is diagnostic doubt at site, the week 3 MRI abdomen scans (and CT chest for M0 patients) a central review will be conducted to determine if a patient has progressed as per RECIST 1.1 criteria. In addition those particular patient cases will be discussed on an individual basis by the trial steering committee (TSC).

The central review for final analysis will be conducted by radiologists based at Addenbrooke's Hospital.

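### Protocol Appendix 6 would read a correlation in one treated arm of at most 20 patients as support for surrogate endpoints, which this design cannot give

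*Protocol*

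**What the plan says.** Section 5.3 (Proteomics) of Protocol Appendix 6 takes protein measurements from two tissue sources: "Formalin fixed paraffin embedded biopsy and nephrectomy tissue will be utilised" for quantified immunohistochemistry. It names Ki67 and CA9 and adds further, unlisted markers of response to tyrosine kinase inhibitors. The intended outcome is to "establish a link between expression of these proteins and reduction in height of the VTT with axitinib". The section ends with the inference at issue: "If a correlation is established these proteins will be helpful as surrogate translational endpoints in future ccRCC neoadjuvant studies".

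The design behind it is set out elsewhere. Protocol section 3.1: "NAXIVA is a single arm, single agent, open label, phase II feasibility study of axitinib". Protocol section 3.4, under Primary Safety Endpoints, caps accrual: "to the final total of 20 patients who have received study drug".

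The neighbouring ctDNA section (Appendix 6, 5.2) closes differently: "Further validation studies of any positive findings will be undertaken separately". Section 5.3 has no equivalent sentence. SAP section 7 presents itself as the full specification of the analysis but contains no proteomic analysis. The one VTT correlation in the SAP (section 7.7) is with total dose received.

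**The concern.** A surrogate endpoint has to do more than correlate with an outcome. The effect of treatment on the marker must predict the effect of treatment on the outcome. With every patient on axitinib there is no contrast between treatments, so this cannot be examined. A correlation within the arm could equally arise because some tumours express less of the protein and also shrink more, whatever the drug does to the protein.

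Section 5.3 adds to the difficulty. It tests several markers, does not say how many, does not define when a correlation counts as established, and asks for no confirmation. At stake is the claim made when the translational results are reported: a chance or purely prognostic association could be described as a surrogate endpoint for later neoadjuvant trials.

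**Working it through.** **The plan's only sized analysis.** Protocol section 9.1 gives a Simon minimax design: 13 then 7 patients, rates 5% against 25%, 10% one-sided, 90% power. Stage 1 stops at 0 improvements, and success needs at least 3 of 20. The probability of success is the chance of 3 or more in 20, less the paths with 0 in the first 13:

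- At 5%: 0.0755 − 0.5133 × 0.00376 = 0.0736, within the 10% limit.
- At 25%: 0.9087 − 0.0238 × 0.2436 = 0.9030.

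The stated design reproduces. It sizes a response proportion, not a correlation or a surrogacy assessment.

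**Precision of a correlation.** Section 5.3 gives no coefficient, level or number of pairs. I assume Pearson's r and a two-sided 5% test; a rank correlation would behave similarly. The number of pairs n cannot exceed 20. It falls if a patient lacks surgery, or lacks usable biopsy tissue when change in expression is the measure.

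Smallest significant r = t/√(n − 2 + t²), with t the 97.5% point on n − 2 degrees of freedom. Fisher interval = tanh(atanh r ± 1.96/√(n − 3)).

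For n = 20: r = 2.101/√(18 + 4.414) = 0.444. Interval: atanh(0.444) = 0.477, ± 1.96/√17 = 0.475, which gives 0.002 to 0.741.

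| Pairs | Smallest significant r | 95% CI at that r |
|---|---|---|
| 20 | 0.44 | 0.00 to 0.74 |
| 16 | 0.50 | 0.00 to 0.80 |
| 15 | 0.51 | 0.00 to 0.81 |
| 10 | 0.63 | 0.00 to 0.90 |

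At n = 20 such a result explains 0.444² ≈ 20% of the variance in VTT reduction. Even an observed r of 0.60 has an interval of 0.21 to 0.82. Approximate power at n = 20 is 41%, 62% and 81% for true correlations of 0.4, 0.5 and 0.6.

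**False hits across markers.** For k independent markers with no true association, the chance of at least one hit at 5% is 1 − 0.95^k:

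- k = 2 (the two named markers): 10%
- k = 5: 23%
- k = 10: 40%
- k = 20: 64%

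The count k is not in the documents, and independence is assumed. Markers measured in the same tissue are likely to be positively correlated, which would lower these figures.

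**Timing.** Protocol section 5.2.7 places the final VTT imaging at day 1 of week 9. Section 5.2.8 places surgery at days 2 to 7 of week 9. The allowed windows overlap, but the order is fixed: the thrombus is imaged before it is removed, and post-treatment protein exists only in the specimen from that operation. The baseline biopsy is earlier, but a baseline value is a candidate predictor, not a surrogate for response.

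**The case against.** The strongest reply is that this is exploratory work described modestly. Appendix 6, section 5, says the techniques may be used to explore and may be replaced by equivalents. The appendix introduction and section 5.3 call the markers putative. The text says the proteins will be helpful; it sets no threshold or decision. This stands as to weight, but it does not rescue the inference. Exploratory status is a reason not to announce a surrogate conclusion in advance.

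Several stronger readings are tempting and should not be drawn:

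- *That the protocol formally qualifies the proteins, or that they will pass into the next trial.* Nothing does this. Protocol section 1.5 makes a phase 3 trial depend on this trial being positive, not on proteomics.
- *That timing rules the protein out altogether.* Section 5.3 never says which outcome the protein would stand in for. Section 1.5 describes a neoadjuvant study without VTT patients, where nephrectomy protein could not be replacing VTT height. The timing argument holds only where VTT change itself is to be replaced.
- *That the CA9 plan is a separate error.* The text says of the sunitinib effect that "this effect will be validated using patient samples from NAXIVA". Protocol section 6.3 uses the same verb for carrying a sunitinib-derived profile over to axitinib, so this is a matter of wording.
- *That false-discovery-rate control is obligatory.* At discovery stage this is a choice. Full listing of markers with intervals meets the need.

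The 5% level is also an assumption: the trial's own convention is 10% one-sided with 80% intervals. Using 10% per marker would raise the false-hit chance, to 1 − 0.90² = 19% for two markers and 1 − 0.90⁵ = 41% for five.

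**Conclusion.** The concern holds as a minor point. A correlation within a single treated arm of at most 20 patients, over several markers, cannot support a surrogacy conclusion, and section 5.3 lacks the confirmation step that section 5.2 has. The lack of a control arm is decisive and needs no assumption. The figures show how weak a just-significant result would be: r = 0.44 with an interval of about 0.00 to 0.74 at 20 pairs, and a false-hit chance of about 10% for two markers and 23% to 64% for 5 to 20. They rest on an assumed two-sided 5% level, all 20 patients giving pairs, assumed marker counts, and independence. A reader might infer that the trial's main result is compromised. It is not, because the proteomic work feeds no primary or secondary endpoint, sample size or stopping rule.

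**What to change.** In Protocol Appendix 6, section 5.3:

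1. Delete the sentence that draws the surrogate-endpoint conclusion.
2. State that every marker tested will be reported, with the number of markers, each marker's rank correlation with percentage change in VTT, and its confidence interval. A false-discovery-rate-adjusted value may be added.
3. Describe any association as a hypothesis-generating candidate response or pharmacodynamic marker.
4. Add the commitment already made for ctDNA in section 5.2, that positive findings will be validated in separate studies.

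The cost is a few sentences and a fuller results table. No extra patients, samples or assays are needed. The only loss is a less favourable claim for an exploratory analysis.
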